## Background

Physical activity is often recommended to reduce the complications associated with obesity, but people living with obesity exercise less than their lean counterparts. Men are more likely to develop obesity related diseases compared with women. Most resources for obesity management are targeting women. Emerging evidences suggest that alternative obesity management strategies need to address gender preferences to adopt healthier lifestyles such as resistance training.

#### Objective

Examine adherence to the physical activity guidelines for men living with obesity who were exposed to a novel circuit weight training program compared with standard care.

#### Design

Sixty men living with obesity will be recruited and randomly assigned to either a standard care group (N = 30) or an intervention group (N = 30). Eligible participants will be age 19 years or older, living with obesity (BF  $\ge$  28%), able to perform exercises, but not currently engaged in regular physical activities (150 min of moderate to vigorous aerobic activities + two sessions of RT per week). Participants will be asked to maintain their current dietary habits within the duration of the project.

### Method

Participants will be asked to come in person to visit the CELLAB at UNB four times (i.e., baseline, 12 weeks, 24 weeks and 48 weeks after baseline; each time for about 90 minutes or do the testing virtually.

Testing done in the CELLAB. During each of the four visit, anthropometric measures (e.g., weight, height, and waist circumference), body composition (e.g., fat and muscle), physical fitness, blood lipids/glucose, and blood pressure will be assessed. Participants will be asked to arrive at the CELLAB at UNB in the morning of the first visit after fasting for a minimum of 12 hours. A small sample of blood will be collected via a finger prick to measure lipids and glucose levels. After recording body composition, a snack will be provided.

When participants leave the CELLAB, they will be asked to wear a Fitbit watch for seven consecutive days (24 hours per day) to quantify their physical activity level. Then, participants

can drop the device at UNB or send it by mail. Four questionnaires will be self-administered to collect information on:

- The perception of the ability to perform exercise using the Self-Efficacy for Exercise (SEE) Scale (Resnick and Jenkins 2000)
- 2- The perceived barriers/benefits to exercise using the Exercise Benefits/Barriers Scale (EBBS) (Sechrist et al. 1987)
- 3- The technology ability using the Functional Assessment of Currently Employed Technology Scale (FACETS) (Lepkowsky and Arndt 2018)

If tests done virtually. If participants do not come to the CELLAB for testing, they will be asked to self-report their weight, height, and waist circumference. At all four time-points, the research team will mail or drop a Fitbit for them to wear for seven consecutive days (24 hours per day) to quantify physical activity level. When the seven days are completed, participants will be asked to drop the device in the nearest Canada Post mailbox using the prepaid envelope. The same questionnaires will be administered.

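### Lipids and glucose are measured at four in-person visits, but the 12-hour fast and morning arrival are set for the first visit only

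*Protocol*

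**What the plan says.** Under Method, the paragraph on testing in the laboratory opens with a list of measures that applies to every visit: "During each of the four visit, anthropometric measures" begins the list, and it ends with "blood lipids/glucose, and blood pressure will be assessed". The same section places the visits at baseline and at 12, 24 and 48 weeks.

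The next sentence gives the only pre-test condition in the document. Participants are to arrive "in the morning of the first visit after fasting for a minimum of 12 hours". Two sentences follow that name no visit: "A small sample of blood will be collected via a finger prick to measure lipids and glucose levels" and "After recording body composition, a snack will be provided".

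The alternative route is remote: "If participants do not come to the CELLAB for testing, they will be asked to self-report their weight", with height and waist circumference also self-reported, plus the activity tracker and the questionnaires. No blood sample is described for that route.

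The only other instruction about eating is in Design: "Participants will be asked to maintain their current dietary habits within the duration of the project". It concerns usual diet over the whole project and sets no fast before a visit.

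**The concern.** The protocol treats fasting state and time of day as worth controlling, because it specifies both. It then repeats the measurement at four visits and attaches the control to one. A site that follows the text exactly would take a fasted morning sample at baseline and samples at weeks 12, 24 and 48 in whatever state, and at whatever hour, the participant arrives.

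Two things would then be at stake. First, within-person change in lipids and glucose would combine any real change with a switch from a controlled to an uncontrolled pre-test state. Second, varying meal timing at follow-up would add variance to the comparison of arms, in a trial with 30 men per arm.

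This is a condition of data collection, not a detail that a statistical analysis plan would supply. Once a sample has been drawn, its fasting state cannot be restored. The document also describes no record of the time since the last meal that could be used for adjustment.

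**Working it through.** The document gives no figure to reproduce on this point. The check is a comparison of sentences followed by a count.

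**Sentences side by side (Method, laboratory testing)**

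| Item | Visits covered by the text |
|---|---|
| Lipids and glucose measured | all four |
| Morning arrival | first only |
| Fast of at least 12 hours | first only |
| Finger-prick sample | none named |
| Snack after body composition | none named |

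The rest of the document (Background, Objective, Design, Intervention, Statistical analysis) contains no other mention of fasting or of time of day at a visit. Nothing says that later samples are meant to be non-fasting.

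**Inputs**

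- Participants: "Sixty men living with obesity will be recruited and randomly assigned", 30 to each group (Design).
- In-person time-points: 4 (Method).
- Time-points with a stated fast and morning arrival: 1 (Method).
- Drop-out assumed for the sample size: 30% in each group (Statistical analysis).

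**Count per participant tested in person**

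- Samples without a stated condition: 4 − 1 = 3, and 3 / 4 = 75%.
- Possible changes from baseline: 3 (weeks 12, 24 and 48). Each pairs a sample with a stated condition with one without.

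**Count for the trial, upper bound (everyone attends all visits in person)**

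- Planned samples: 60 × 4 = 240.
- With a stated condition: 60 × 1 = 60.
- Without: 60 × 3 = 180, which is 75% of 240. Per arm: 30 × 3 = 90 of 30 × 4 = 120.

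**Allowing for the protocol's own drop-out assumption**

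- Completers: 60 × (1 − 0.30) = 42.
- Follow-up samples from completers, all tested in person: 42 × 3 = 126.
- With 30% drop-out and no virtual testing, the number without a stated condition is therefore at least 126. It is higher to the extent that men who leave attend some follow-up visits first, and it stays below 180. Virtual testing lowers it further, by an amount the document does not let one estimate.

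These are counts of samples exposed to the gap, not effects. The document gives no variance, correlation or prandial effect for lipids or glucose, so no bias or loss of precision can be calculated.

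**The case against.** The strongest reply is that this is a slip of wording and not a decision. The phrase sits in a paragraph that opens with all four visits and goes on to a finger prick and a snack that are not tied to any one visit. A snack after testing fits a participant who has fasted each time. That reading is plausible, but it does not remove the problem. The text names the first visit explicitly, and staff and participants act on what is written. If the fast was meant for every visit, the sentence misstates the intent. If it was not, follow-up samples are not comparable with baseline.

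The second reply is that no stated inference depends on it. This stands. The Objective, the main outcome, the logistic model and the sample size all concern the physical activity guidelines. The document names no lipid or glucose endpoint and does not say that a change from baseline will be analysed. The point therefore bears only on supporting measures.

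The third reply is that randomisation protects the comparison of arms. This stands as far as bias is concerned: the condition is worded identically for both groups, and bias would need fasting to differ by arm, which nothing in the document suggests. It does not answer the added noise or the loss of comparability within person.

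Finally, the noise could be partly adjusted for if fasting state were recorded. That is correct in principle, but the document describes no such record.

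**Conclusion.** The concern holds, as a minor point. The protocol measures lipids and glucose at four in-person visits and states a fast and a morning arrival for one, which leaves three of four samples per in-person participant without either condition. The trial total is at most 180 of 240, and fewer with drop-out or virtual testing.

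Any harm depends on later visits being unfasted in practice and on the lipid or glucose results being used to describe change or to compare arms. The document establishes neither. If later visits are fasted anyway, the loss is zero. If not, the consequences are contaminated within-person change and a noisier comparison between arms, of a size that cannot be derived here. No bias between arms is claimed, and the main outcome is not affected. Confidence is medium, because a drafting slip is a reasonable explanation.

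**What to change.** Reconcile the two sentences under Method. The direct way is to apply the protocol's existing condition (morning arrival, fast of at least 12 hours) to every in-person visit at which blood is taken, by making the sentence refer to each visit instead of the first. This introduces no new rule. Optionally, record the hours since the last meal at every sample, so that fasting state can be checked and, if needed, used in the analysis.

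The cost is one phrase and one optional data field. The real burden falls on participants, who would fast before three more visits, and the sponsor should weigh that against the use intended for these measures. The change helps only samples not yet taken, so it should be made before follow-up visits begin.

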#### Intervention

RT+ program. Participants in RT+ group will be asked to exercise three times per week and perform four basic RT exercises in a circuit manner for 12 weeks while supervised via an online platform such as Skype or TEAM. Before starting the 12-week program, each participant will receive an educational session explaining and teaching RT+ exercises. During this session, the participant will go though the exercises to make sure he knows how to preform RT+ exercises correctly and modifications will be applied if needed based on participants conditions. The first week of sessions will be in person supervised. Participants will be eased into the program using a three-week progressive start, completing 120 minutes of exercise in week one, 150 minutes in week two, 180 minutes in week three and week four. Participants will be supervised 3X/week for the first four weeks, then 2X/week for the next four weeks and 1X/week for the remaining four weeks. This strategy has been successfully used previously to increase participant autonomy before they start the unsupervised phase. At each session, a participant will perform the four prescribed exercises (i.e., squats, tricep dips, lunges, and push-ups) for 45 seconds each, then switch immediately (15 seconds) to the next exercise followed by one-minute of rest at the end of each

circuit. The circuit will repeat until the session is complete. If a participant has restrictions that prevent him from performing an exercise, modifications will be made.

Standard care (control). Participants allocated to the control standard care group will receive free access to an exercise platform (V-Shred-Ripped-in-90-days) for the same period of time (12 weeks) to become more active. It will be recommended that they do a minimum of 150 minutes of moderate to vigorous aerobic activities and two resistance training sessions using the platform.

#### Statistical analysis

Sample size calculations was done based on the anticipated change in the proportion of obese men to achieve the PA guidelines (minimum of 150 minutes spent at MVPA in a week in addition to two sessions of RT). It is predicted that the proportion of men living with obesity who meet physical activity guidelines (both aerobic MVPA and RT) in the RT+ group will increase to 26.2% (similar to lean counterparts) at follow-up compared with 0% increased for the control group. The alpha level and power of analysis were set at 0.05 and 80% respectively, considering a drop-out rate of 30% in each group. A total of 23 people per group were required, so we will recruit 30 per group.

To evaluate the effect of the intervention on the main outcome (% of people reaching the PA guidelines 36 weeks after the intervention), a logistic regression model will be used. The independent variables will include age, PA level at baseline, the randomized group, and other potential confounding variables.

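### The 80% power rests on an unexplained, best-case 0% control rate and on 23 men per group, while the stated dropout leaves 21

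*Protocol*

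**What the plan says.** All the planning values are in the Protocol, Statistical analysis. The calculation rests on the "anticipated change in the proportion of obese men to achieve the PA guidelines". The RT+ proportion "will increase to 26.2% (similar to lean counterparts) at follow-up", "compared with 0% increased for the control group". Alpha is 0.05 and power 80%, "considering a drop-out rate of 30% in each group". The result is: "A total of 23 people per group were required, so we will recruit 30 per group". The main outcome is the percentage "of people reaching the PA guidelines 36 weeks after the intervention", analysed by logistic regression.

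Two other sections bear on the 0%. The Design section restricts entry to men who do not already reach the combined target of 150 minutes of aerobic activity plus two resistance sessions a week. The Intervention section, under standard care, gives controls free access to an exercise platform "for the same period of time (12 weeks) to become more active", and adds: "It will be recommended that they do a minimum of 150 minutes of moderate to vigorous aerobic activities and two resistance training sessions".

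**The concern.** With a baseline of zero by eligibility, a 0% increase means that not one control man meets the guideline at follow-up. The section gives a short reason for 26.2% (parity with lean men) and none for 0%. Yet the control arm receives an exercise resource and is advised to do the same two things that define success.

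Zero is also the best case for power. With the RT+ rate fixed, it gives the largest difference. With the difference fixed, it gives the smallest variance. Any control success rate above zero therefore reduces power, and in a trial this small the loss may be large. The allowance for dropout needs checking too, because it decides how many men the power figure applies to.

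What is at stake is interpretation. If the comparison is not significant, a reader who relies on the stated 80% would give that result more weight as evidence against RT+ than the design may support.

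**Working it through.** **Inputs.** From the Statistical analysis section: RT+ rate 0.262, control rate 0, alpha 0.05, power 80%, 23 required and 30 recruited per group, dropout 30%. Sidedness and formula are not stated. Control rates of 2% and 5% are assumptions made here, because the Protocol gives no alternative to 0%.

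**1. Reproducing the 23.** Unpooled normal approximation, two-sided:

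n = (1.960 + 0.842)² × [p1(1−p1) + p0(1−p0)] / (p1−p0)² = 7.849 × (0.262 × 0.738 + 0) / 0.262² = 22.1, rounded up to 23.

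This matches exactly. The pooled two-sided version gives 25 and the continuity-corrected version 32. The unpooled formula is therefore an inference from the match.

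**2. Power by that formula.** Power = Φ(|p1−p0| / √{[p1(1−p1) + p0(1−p0)]/n} − 1.960). At 23 per group and 0% control: 0.262 / √(0.193356/23) = 2.857, and Φ(2.857 − 1.960) = 81.5%.

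| Control rate | RT+ rate | 21 per group | 23 per group | 30 per group |
|---|---|---|---|---|
| 0% | 26.2% | 78% | 81.5% | 90% |
| 2% (assumed) | 26.2% (fixed) | 67% | 71% | 82% |
| 5% (assumed) | 26.2% (fixed) | 51% | 54% | 66% |
| 2% (assumed) | 28.2% (difference kept) | 72% | 76% | 86% |
| 5% (assumed) | 31.2% (difference kept) | 65% | 69% | 80% |

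**3. Does the result depend on the approximation?** With close to zero expected control successes, a normal approximation is rough. Exact power was found by applying each two-sided 5% test to every possible pair of counts and summing the binomial probabilities. RT+ is fixed at 26.2%:

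| Control rate | n per group | Fisher | Chi-square | Likelihood ratio |
|---|---|---|---|---|
| 0% | 23 | 76% | 89% | 96% |
| 2% | 23 | 60% | 75% | 79% |
| 5% | 23 | 41% | 55% | 57% |
| 0% | 21 | 68% | 84% | 94% |
| 2% | 21 | 53% | 70% | 76% |
| 5% | 21 | 36% | 51% | 54% |

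The first row can be checked by hand. With no control successes, significance at 23 per group needs at least 5 RT+ successes under Fisher, 4 under chi-square and 3 under the likelihood ratio. For a binomial with n = 23 and p = 0.262, these events have probability 75.9%, 88.9% and 96.2%.

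The level therefore depends on the test, but the fall from 0% to 5% is about 34 to 39 points under every one. All of these are unadjusted comparisons; power for the covariate-adjusted logistic model cannot be computed from the document.

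**4. Dropout.** 30 × (1 − 0.30) = 21, which is below 23. Keeping 23 after 30% loss needs 23/0.70 = 32.9, so 33 per group. The planned 30 corresponds to 23 × 1.3 = 29.9, which adds 30% of 23 and does not allow for losing 30% of those recruited.

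**The case against.** The strongest reply is that the control rate may well be close to zero. No supervision of controls is described, platform access lasts 12 weeks, and the outcome is a demanding combined target assessed 36 weeks after the intervention. This stands: 0% is an optimistic planning value, not an error of fact.

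It also stands that recruitment is 30 per group. If all 30 were analysed, the same formula would give 82% or 86% at a 2% control rate. That requires no dropout, however, whereas the plan itself expects 30%. At 5% with RT+ fixed, even 30 per group gives 66%.

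A reader might infer four stronger points that the document does not support:

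- *That the 0% condition is undisclosed.* It is not. The section says what the calculation was based on and states the 0% openly. What is missing is a reason for it and any indication of how much the power depends on it.
- *That power falls below 80% as soon as the control rate exceeds a few tenths of a percent.* Such a threshold comes from the approximation. By exact calculation, chi-square and the likelihood ratio start above 80% at 0%, while Fisher at 23 per group never reaches it.
- *That one control success among 21 men, 4.8%, would show the power to have been little more than half.* An observed count is not the true rate. At a true rate of 2%, at least one success among 21 has probability 1 − 0.98²¹ = 35%.
- *That the protocol's own formula gives these powers.* The protocol names no formula.

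**Conclusion.** The point holds as a weakness in a stated planning value, together with an arithmetic slip in the dropout allowance.

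- **Control rate.** The 0% is the most favourable value, has no stated rationale, and sits beside a control arm advised to do both endpoint components. By the inferred formula at 23 per group, moving from 0% to an assumed 2% costs about 10 points (RT+ fixed) or 6 points (difference kept). Moving to 5% costs about 27 or 13 points. The direction and steepness do not depend on the test; the exact level does.
- **Dropout.** The stated 30% leaves 21 per group, two fewer than the plan says it needs. At 0% control this costs about 4 points by the formula (81.5% to 78%). Exact power at 21 per group and 0% is 68% (Fisher), 84% (chi-square) or 94% (likelihood ratio), so whether 80% is met there depends on a test that the section's calculation does not identify.

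This rests on the assumed 2% and 5% control rates, the inferred two-sided unpooled formula, unadjusted comparisons, and dropout occurring as planned. It does not show that the control rate will exceed zero or that the trial is too small to run.

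**What to change.** Keep the sample size. In the Protocol, Statistical analysis:

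- correct the statement that 30 per group covers 30% dropout from a requirement of 23, and give the expected 21 per group;
- name the test, sidedness and formula behind the sample size;
- give the reason for the 0% control rate, or say that it is an optimistic assumption;
- restate power at 21 per group by the named method, at 0% and at a few low control rates labelled as assumptions (for example 2% and 5%), both with RT+ fixed at 26.2% and with the 26.2-point difference kept;
- state that the 80% should not be used to read a non-significant result as evidence of no effect.

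The cost is a few sentences and a short table, with no extra participants or procedures. The downside is a less favourable stated power.

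### With 30% drop-out, 30 recruited per group leaves 21 completers, not the 23 the protocol says it needs; the allowance appears to have been multiplied on (× 1.3) instead of divided out (÷ 0.7)

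*Protocol*

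**What the plan says.** The protocol's Statistical analysis section sizes the trial on the proportion of men who meet the physical activity guidelines. It predicts that this proportion "in the RT+ group will increase to 26.2% (similar to lean counterparts) at follow-up", "compared with 0% increased for the control group". It adds: "The alpha level and power of analysis were set at 0.05 and 80% respectively", "considering a drop-out rate of 30% in each group". The result is given in one sentence: "A total of 23 people per group were required, so we will recruit 30 per group". The Design section has the same target, 60 men split 30 and 30. The protocol gives no other drop-out rate or recruitment target. It names no sample-size formula or test and does not say whether alpha is one- or two-sided.

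**The concern.** The concluding sentence presents 23 as the number needed and 30 as the number to recruit so that 23 are left after losses. A 30% loss is a fraction of those recruited, so the required number has to be divided by 0.7. Multiplying by 1.3 adds 30% of the smaller number, which is too little. If that was done, the trial would miss its own required size at exactly the drop-out rate it planned for, and its claim of 80% power would not be true on its own terms.

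Drop-out matters for this outcome, because it is assessed 36 weeks after a 12-week programme.

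**Working it through.** **Inputs** (Statistical analysis section unless noted)

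- RT+ proportion p₁ = 0.262.
- Control proportion p₀ = 0. The text speaks of a 0% increase; under the Design section, eligible men do not meet the guidelines at entry, so this is taken as 0%.
- Alpha 0.05, taken as two-sided; power 80%.
- Drop-out 30% per group.
- Allocation 1:1, 30 per group (Design).

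**Step 1: reproduce the 23.** The unpooled normal formula is

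n = (z₀.₉₇₅ + z₀.₈₀)² × [p₁(1 − p₁) + p₀(1 − p₀)] / (p₁ − p₀)²

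= (1.96 + 0.8416)² × (0.262 × 0.738) / 0.262² = 7.849 × 0.19336 / 0.06864 = 22.1, so 23 per group.

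This matches the stated requirement with no drop-out included. The pooled-variance version gives 24.8, so 25.

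**Step 2: reproduce the 30.**

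- Multiplying: 23 × 1.3 = 29.9, so 30, the stated figure.
- Dividing: 23 / 0.7 = 32.9, so 33.

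The protocol does not show this step, so the multiplication is an inference. The next step does not depend on it.

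**Step 3: completers under the plan.**

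- 30 × 0.7 = 21 per group, against 23 required: 2 short.
- 33 × 0.7 = 23.1 per group, which meets 23.
- Largest drop-out at which 30 per group still leaves 23: (30 − 23) / 30 = 23.3%.
- Recruits missing: 33 − 30 = 3 per group, 6 in total.

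**Step 4: effect on power**, 26.2% versus 0%, two-sided 0.05.

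| Method | 23 per group | 21 per group |
|---|---|---|
| Unpooled normal (reproduces 23) | 81.5% | about 78% |
| Pooled normal | 76.8% | 72.7% |
| Fisher's exact test | 75.9% | 67.9% |
| Pearson chi-square, evaluated exactly | 88.9% | 84.0% |

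For the first row at 21: Φ(0.262 / √(0.19336 / 21) − 1.96) = Φ(2.730 − 1.960) = Φ(0.770), about 0.78.

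**Step 5: the other reading.** Suppose 23 already includes drop-out. Then 23 × 0.7 = 16.1, so about 16 men per group complete. Power at 16 is 66% by the unpooled formula and 60% by the pooled one, both well below 80%.

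**The case against.** The strongest reply is that the protocol never says 23 means completers. The drop-out clause comes before the 23, so 23 could already allow for drop-out, with 30 as a further margin. Rejecting that reading by the unpooled formula is partly circular, since that formula was chosen because it gives 23 before drop-out.

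Another method does support the alternative. An unadjusted likelihood-ratio test, evaluated exactly, has 79.5% power at 15 per group and 83.1% at 16, so 16 is the smallest adequate number, and 16 / 0.7 = 22.9 rounds up to 23. On that basis 21 completers are ample: power is 94.1%, and the arcsine formula gives 93.6%. None of the methods above is the planned analysis, which is a covariate-adjusted logistic regression.

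Part of this stands. The multiplication by 1.3 is inferred, power at 21 depends heavily on the method, and it cannot be said that every test falls below 80%. The alternative reading is nevertheless the weaker one. It leaves the step from 23 to 30 without a reason, although the sentence presents 30 as following from 23. It also relies on a test that can exceed its nominal alpha in samples this small. The reading used here explains both stated numbers with one formula and one common slip.

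It is also fair to say that the effect is small and that recruitment, endpoint and analysis need not change. That bears on the choice of remedy and does not make the sentence correct.

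**Conclusion.** The point holds. As written, 30 per group does not deliver the stated requirement of 23 at the stated 30% drop-out; it delivers 21. The shortfall is 2 completers per group, or 6 recruits in total. On the formula that reproduces 23, power is about 78%, roughly 2 points under the 80% target and 3.6 points under the 81.5% that 23 completers would give.

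The shortfall in completers rests only on reading 23 as the number needed after losses, which is how the sentence presents it. The power figures rest in addition on a two-sided alpha, a control proportion of 0% and the unpooled formula, and other tests move them in either direction. The defect is a small but plainly wrong statement about the only sample size the protocol gives.

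**What to change.** Keep 30 per group and correct the sentence in one of two ways:

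- state that 30 per group retains the required 23 provided drop-out is no more than 23%; or
- state that at 30% drop-out 21 per group remain, with about 78% power on the same formula.

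In either case, say that 23 is the number before drop-out, name the formula or test, and state whether alpha is two-sided. If the sponsor arrived at 23 by another route that already includes drop-out, that route and the reason for going from 23 to 30 should be written down instead.

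The cost is one reworded sentence and a slightly less favourable stated figure; no extra participants are needed. Only if 30% drop-out and 80% power are both to stand on this formula does the target become 33 per group, 66 in total, which is 6 more men than planned, and the Design section would then have to change as well.

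### The planned primary logistic regression has no finite group odds ratio in the scenario the trial was sized for (0% control response, about 6 events)

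*Protocol*

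**What the plan says.** The Statistical analysis section defines the main outcome as the percentage "of people reaching the PA guidelines 36 weeks after the intervention". For its analysis, "a logistic regression model will be used. The independent variables will include age, PA level at baseline, the randomized group" and, as an open-ended addition, "and other potential confounding variables". The fitting method, test and type of interval are not given.

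The sample-size paragraph of the same section predicts that the proportion meeting the guidelines "in the RT+ group will increase to 26.2% (similar to lean counterparts) at follow-up", "compared with 0% increased for the control group". It continues: "considering a drop-out rate of 30% in each group. A total of 23 people per group were required", with 30 per group to be recruited.

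Two other sections bear on the control rate. Design admits men "not currently engaged in regular physical activities (150 min of moderate to vigorous aerobic activities + two sessions of RT per week", so nobody meets the combined target at entry. Intervention says of the control group: "It will be recommended that they do a minimum of 150 minutes of moderate to vigorous aerobic activities and two resistance training sessions".

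**The concern.** Nobody meets the target at baseline, so a 0% increase in control means 0% at follow-up. The planning scenario is therefore a two-by-two table with an empty control cell, and the next paragraph names a model whose usual estimate does not exist for such a table. If the trial succeeds as predicted, an ordinary fit gives no usable odds ratio or confidence interval for its main outcome, and default Wald output would show a p-value near 1 for a clear difference. The choice of test would then be made after the data are seen, when the candidate tests give very different answers. The open covariate list adds to the difficulty, because about 6 events cannot support many terms.

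**Working it through.** **Inputs.** From Statistical analysis: RT+ 26.2%, control 0%, alpha 0.05 (taken as two-sided), power 80%, 23 per group required, 30 recruited, 30% drop-out. Retained per arm: 30 × 0.70 = 21. Control rates of 2%, 5% and 10%, and all common null rates, are assumptions.

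**1. The plan's own figure.** The unpooled two-proportion formula gives n = (1.960 + 0.842)² × (0.262 × 0.738 + 0) / 0.262² = 22.1, rounded up to 23. This matches the protocol, so 26.2% v 0% is the scenario used for sizing.

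**2. Expected events.** 23 × 0.262 = 6.0, or 21 × 0.262 = 5.5, all in RT+.

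**3. The fit at 6/23 v 0/23.** The maximum-likelihood group log-odds does not converge. Stopped at 8, 15 and 25 iterations it is 8.5, 15.5 and 25.5, with standard errors 15, 500 and 74,257 and Wald p of 0.57, 0.975 and 0.9997.

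**4. Other methods on the same table.** Under the null, each arm expects 3 events and 20 non-events.
- Likelihood ratio: 2 × [6 ln(6/3) + 17 ln(17/20) + 23 ln(23/20)] = 9.22, p = 0.002; profile interval 3.3 to infinity.
- Score: 9/3 + 9/3 + 9/20 + 9/20 = 6.90, p = 0.009.
- Firth (here equivalent to adding 0.5 to each cell): (6.5 × 23.5) / (17.5 × 0.5) = 17.5; profile interval 1.9 to 2334, p = 0.008.
- Exact: median-unbiased odds ratio 10.2 (1.35 to infinity); Fisher p = 0.022.
- Risk difference: 6/23 = 26 points; Miettinen-Nurminen score interval 10 to 47.

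**5. Probability of an empty control cell at 21 per arm.** 0.98²¹ = 65%, 0.95²¹ = 34%, 0.90²¹ = 11%; it is 100% at the planned 0%.

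**6. Unadjusted power, RT+ 26.2%, 21 per arm.** All two-by-two tables were enumerated exactly, with Wald counted as non-significant when a cell is zero.

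| Control rate | Wald | Likelihood ratio | Score | Firth |
|---|---|---|---|---|
| 0% | 0% | 94% | 84% | 84% |
| 2% | 9% | 76% | 70% | 70% |
| 5% | 15% | 54% | 51% | 51% |
| 10% | 14% | 29% | 28% | 28% |

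At 23 per arm, Wald gives 0/13/20/17%, likelihood ratio 96/79/57/31%, and score and Firth 89/75/55/31%.

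**7. Unadjusted type I error, 21 per arm**, at common rates of 2%, 5%, 10% and 13.1%: likelihood ratio 1.1%, 5.8%, 8.5% and 7.4%; score and Firth 0.1%, 1.3%, 4.1% and 4.9%.

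**8. With covariates.** 8,000 simulated trials per setting, with independent standard-normal covariates that have no effect. At 26.2% v 0%, two covariates and 21 per arm, power is 93% for likelihood ratio, 84% for score and 75% for Firth; Firth reaches 80% at 23 per arm. With five covariates at 21 per arm, Firth falls to 66.5% and likelihood ratio to 87.7%. Type I error with two covariates at 13.1% in both arms is 8.8%, 6.3% and 4.2% for likelihood ratio, score and Firth.

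**The case against.** The strongest reply is that fitting method, test and interval usually belong in an SAP, which is not at hand, and that a Firth, exact, likelihood-ratio or score analysis would all fit the words used. The protocol commits to neither Wald nor unpenalised likelihood. That is right as far as it goes: the hypothesis test is not broken by the stated plan. What remains is a mismatch within one section, which itself fixes both the 0% control rate and the model. Changing the test does not repair the estimate, because the likelihood-ratio and score tests still leave the odds ratio infinite.

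Second, 0% is a prediction, and controls are given a platform and advised to reach the same target, so some may respond. This also stands. The estimate is then generally finite, and at an assumed 10% an empty cell has only an 11% chance. Low power at that rate is also partly the smaller effect: Firth has 28% and likelihood ratio 29%, against 14% for Wald.

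Third, Firth is not the only remedy. Its upper limit of 2334 tells a reader little more than infinity, and adjusted at 21 per arm it has 75% power against 84% for the score test and 93% for likelihood ratio. The trade-off is real. Likelihood ratio obtains part of its advantage from a type I error of up to 8.8%, and the adjusted score test was at 6.3% where Firth held 4.2%. The wide limit is the reason to report a risk difference as well. The adjusted figures assume covariates without effect and are illustrative.

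**Conclusion.** The concern holds and should be fixed. In the planned scenario the ordinary fit of the stated model yields an infinite group odds ratio and a useless Wald interval, whatever the RT+ count. This is certain with zero control responders and remains likely (65% at 21 per arm) if the true control rate is 2%. The defect lies mainly in the estimate and interval. For the test, the harm is that an unspecified choice spans p = 0.002 to 0.999 on a single plausible table. The mechanism and the figures at 0% and 26.2% follow from the protocol, taking alpha as two-sided; the results at other control rates and with covariates rest on the assumptions stated above.

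**What to change.** State that the primary model is Firth (penalised-likelihood) logistic regression, tested by the penalised likelihood-ratio test rather than Wald, with a profile-likelihood interval. Report the risk difference with a score or exact interval beside the odds ratio. Replace the open list of confounders with three terms: randomised group, age and baseline activity level. Exact logistic regression is an alternative, but its upper limit stays infinite at zero control events.

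The change is one or two sentences and a standard software option; design and recruitment are untouched. The costs are slight shrinkage of the estimate, a very wide upper limit, no adjustment for further covariates, and less power than likelihood ratio (84% v 94% unadjusted, about 75% v 93% with two covariates, at 21 per arm). Limiting the covariates matters because five of them reduce Firth power to about 67%.
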